6.3.2. Drugs

Drugs will be coded with WHO (ATC coding system) Drug version Sep-2020 (or newer if available).

6.3.3. Classification criteria

Adverse Events will be graded for severity using the classifications of National Cancer Institute Common Terminology Criteria for Adverse Events version 5.0 (NCI CTCAE v5.0).

6.4. Report type, language, format

The statistical output will be in pdf format and presented in English language.

The following criteria will be used:

- Dates will be presented with the DDMMYY format.
- Counts and percentages:

<group 1> XX (XX.X%)

Note: for Adverse Events tables percentages will be displayed with two decimal places.

- Descriptive statistics:

N	XX
Mean	XX.XX
Median	XX.XX
SD	XX.XXX
Minimum	XX.X
Maximum	XX.X

In general, the following rule will be applied for decimal place:

- Minimum, maximum: one decimal place
- Arithmetic mean and median: one more decimal than minimum/maximum
- SD: one more decimal than arithmetic mean/median
- N: no decimal

Character will be left aligned.

6.5. Standard Operating Procedures (SOPs) to be followed

¹ Code	Title
MR-GCS-DMST-210_SOP	Statistical Analysis Plan (SAP)
MR-GCS-DMST-211_SOP	Statistical Programs Writing
MR-GCS-DMST-211.3_WI	TLF programming

6.6. Data Transfer Agreements

Sysmex Mutational/Molecular Data

Data Transfer Agreement (DTA) between Sysmex Inostics GmbH and Menarini Ricerche S.p.A., version 1.0 effective 21st Jan 2022.

CTC Immunology Data

Data Transfer Agreement between Menarini Silicon Biosystems and Menarini Ricerche S.p.A., version 1.0 (22nd Jun 2020).

Data Management Plan

Data Management Plan version 2.0 (10th Mar 2021).

Pharmacokinetics data

PK concentrations Data Transfer Agreement (DTA) between Clinical Laboratory and Data Management & Clinical Sciences unit of Menarini Ricerche S.p.A., version 1.0 of 15th July 2020.

CTC data

CTC results Data Transfer Agreement (DTA) between Clinical Laboratory and Data Management & Clinical Sciences unit of Menarini Ricerche S.p.A., version 1.0 of 14th July 2020.

7. Definitions and general methodology

7.1. Data quality assurance

All tables, figures and data listings to be included in the report will be independently checked for consistency, integrity and in accordance with Menarini Ricerche standard procedures.

7.2. General considerations and key definitions

7.2.1. General considerations

Study day is defined as the number of days from the date of first dose of study treatment to the event/visit date. For dates equal to or later than the first dose of study treatment, study day is calculated as follows:

Study Day = Event or Visit Date – First Dose Date + 1

For dates prior to the first dose of study treatment, study day is calculated as follows:

Study Day = Event or Visit Date – First Dose Date

One (1) month will be considered to be equal to 30.4375 days when calculating durations or survival times in months.

7.2.2. Key definitions

Baseline values

The baseline value of an assessment is defined as the value measured before the first study drug administration at Visit 1 of Cycle 1. If the pre-infusion value at Visit 1 is missing or not done, the value measured during the Screening Visit is considered as baseline value.

Adverse Events (AEs)

Any untoward medical occurrence in a patient or clinical study patient administered a medicinal product and which does not necessarily have a causal relationship with this treatment. An AE can therefore be any unfavourable and unintended sign (including an abnormal laboratory finding), symptom, or disease temporally associated with the use of a medicinal product, whether or not considered related to the medicinal product.

Treatment-Emergent Adverse Events (TEAEs)

If an AE occurs for the first time or if it worsens in terms of seriousness or severity after the first study treatment (either MEN1611 or cetuximab) intake, it will be classified as TEAE, otherwise it will be classified as non-TEAE.

AEs that have missing onset dates will be considered to be treatment-emergent, unless the stop date is known to be prior to the first administration of the study medication.

Adverse Drug Reactions (ADRs)

An adverse drug reaction (ADR) in this study is defined as any adverse event (AE) suspected by the Investigator and/or the Sponsor to be related to MEN1611, cetuximab or both given in combination. Toxicities will be graded according to the NCI CTCAE v5.0, except for segmental wall-motion abnormalities (not described in NCI CTCAE v5.0).

All AEs (including SAEs) are to be accurately recorded on the AE page of the patient's eCRF. Each event will be graded for severity using the classifications of NCI CTCAE v5.0. For events not addressed in the NCI CTCAE v5.0 classification, the following grading will apply:

- **Mild (Grade 1)** - Mild; asymptomatic or mild symptoms; clinical or diagnostic observations only; intervention not indicated;
- **Moderate (Grade 2)** - Moderate; minimal, local or noninvasive intervention indicated; limiting age-appropriate instrumental activity of daily living;
- **Severe (Grade 3)** - Severe or medically significant but not immediately life-threatening; hospitalization or prolongation of hospitalization indicated; disabling; limiting self-care activity of daily living;
- **Life-threatening (Grade 4)** - Life-threatening consequences; urgent intervention indicated.
- **Death (Grade 5)** - Related to adverse event.

NOTE: In case of an AE/ADR consisting of a laboratory abnormality, its intensity (severity) should be ranged based on the level of abnormality of the out-of-range value and/or its interference on patient ability to perform daily routine activities, as above defined. A severe AE, as defined by the above grading scale, is NOT the same as serious AE.

Serious Adverse Event (SAE) / Serious Unexpected Adverse Reaction (SUSAR)

Any SAE judged by the Investigator or the Sponsor as drug-related and considered as unexpected is qualified as a Suspected Unexpected Serious Adverse Reaction (SUSAR). SUSARs are subject to expedited reporting, as having a “Reasonable Possibility” of relationship with the study treatment (MEN1611, cetuximab or their combination).

Any untoward medical occurrence or effect that at any dose:

- results in death.
- is life-threatening.

Note: the term life-threatening in the definition of “serious” refers to an event in which the patient was at risk of death at the time of the event; it does not refer to an event which hypothetically might have caused death if it were more severe.

- requires patient hospitalization or prolongation of existing hospitalization.
- results in persistent or significant disability/incapacity.
- is a congenital anomaly/birth defect.
- is an ‘important medical event’ that may jeopardize the patient or may require an intervention to prevent one of the above characteristics/consequences.

Note: Hospitalization lasting less than 24 hours or pre-planned hospitalization for medical intervention, such as chemotherapy administration, shall not qualify as SAE.

Any other AE/ADR which is not included in the above definitions will be considered as non-serious. The Investigator should also promptly report all the SAEs to the Sponsor’s Drug Safety Manager.

Algorithm for Causality Assessment of Adverse Events

The relationship between an AE and study treatments will be judged according to the following categories:

- **Certainly related:** The event or laboratory test abnormality (AE) has a plausible time relationship to the drug intake and it cannot be explained by a concurrent disease or other drugs. The response to withdrawal of the drug (dechallenge) should be plausible (pharmacologically, pathologically). The event must be definitive pharmacologically or phenomenologically (i.e. an objective and specific medical disorder or a recognised pharmacological phenomenon), using a satisfactory rechallenge procedure if necessary.
- **Probably related:** The event or laboratory test abnormality (AE) with reasonable time relationship to the drug intake, it is unlikely to be attributed to a concurrent disease or other drugs and it follows a clinically reasonable response on withdrawal

(dechallenge). Rechallenge (AE reappearance after drug reintroduction) is not required to fulfil this definition.

- **Possibly related:** The event or laboratory test abnormality (AE) has a reasonable time relationship to the drug intake, but it could also be explained by disease or other drugs. Information on drug withdrawal (dechallenge) may be lacking or unclear.
- **Unassessable/Unclassifiable:** The relationship cannot be judged, because of the information is insufficient or contradictory and data cannot be supplemented or verified.
- **Unlikely related:** The event or laboratory test abnormality (AE), with a time to drug intake that makes a relationship improbable (but not impossible). Disease or other drugs provide plausible explanations.
- **Not Related:** The event or laboratory test abnormality (AE), with a time to drug intake with an unreasonable relationship and or non-plausibility and/or the existence of a clear alternative explanation.

In case of disagreement between the Investigator and the Sponsor's Medical Monitor, the more conservative assessment will determine the relationship outcome.

An AE in which the relationship is ranked 1, 2, 3 or 4 is defined as an ADR. AEs ranked 5 or 6 are not considered as ADRs.

7.3. Analysis populations

The following analysis populations will be considered in the statistical analysis:

- Safety population: all patients receiving at least 1 dose of MEN1611.
- DLT population: All patients receiving at least 80% of MEN1611 and 75% of cetuximab during Cycle 1 with a Safety Follow-up of 28 days after the first administration of the study treatment. Any patient who experiences a DLT will also be considered evaluable, regardless of the dose received. Patients enrolled in the Dose-confirmation Phase, who are not DLT evaluable, will be replaced. DLT Population is applicable only for the dose escalation phase patients, thus all Cohort Expansion patients will be not part of this population.
- Efficacy population: all eligible patients who receive at least 2 complete treatment cycles and have at least 1 disease assessment are to be considered evaluable for efficacy.
- PK population: All patients receiving MEN1611 and for whom a PK sample is obtained and analysed.

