8.2.3.2 Withdrawal from the Study Treatment

Patients will be withdrawn from the study treatment if they experience:

- Any protocol deviation which in the opinion of the Investigator or the Sponsor exposes the patient to risk by continuing the treatment.
- Any medical condition or personal circumstance or AE with a possible, probable or certain drug-causality as per Investigator's judgement which exposes the patient to risk by continuing the treatment.
- Disease progression.
- Delay in scheduled treatment exceeding 21 days due to study drug related toxicity.
- Occurrence of pregnancy.
- Patient's request.

All patients shall undergo the End of Study Visit at the time of study withdrawal or discontinuation of the study treatment. Unscheduled assessments showing disease progression and leading to patient's withdrawal can replace the End of Study Visit provided that all assessments/procedures scheduled for this visit are completed.

If a patient prematurely terminates the study as per patient's request, data already collected will be used and analysed for the purpose of the study, as per local regulation.

In case of withdrawal of consent, the patient may choose if samples/images which are already collected but not analysed yet, can be analysed or shall be destroyed.

During the Dose-confirmation Phase, patients not evaluable for DLT will be replaced.

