9 STATISTICAL METHODS AND DETERMINATION OF SAMPLE SIZE

9.1 Determination of Sample Size

9.2 Analysis Populations

DLT population:

All patients receiving at least 80% of MEN1611 and 75% of cetuximab during Cycle 1 with a Safety Follow-up of 28 days after the first administration of the study treatment. Any patient who experiences a DLT will also be considered evaluable, regardless of the dose received.

Patients enrolled in the Dose-confirmation Phase, who are not DLT evaluable, will be replaced.

Safety population:

All patients receiving at least 1 dose of MEN1611.

Efficacy population:

All eligible patients who receive at least 2 complete treatment cycles and have at least 1 disease assessment are to be considered evaluable for efficacy.

PK population:

All patients receiving the study treatment and for whom a PK sample is obtained and analysed.

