11.2. Descriptive statistics

All study variables (with the exception of PK variables) will be presented by dose cohort and

overall, using the appropriate descriptive statistics according to the variable nature, unless otherwise specified:

- **Continuous variables:** Number of non-missing observations, arithmetic mean, standard deviation, minimum, median and maximum.
- **Categorical variables:** Number of non-missing observations and column percentages (N, %).
- **Time to event variables:** Number of non-missing observations, number and percentage of censored observations, 1st quartile, median (and its 95% CI), 3rd quartile, Kaplan-Meier survival curves and event rate every 28 days.

The behaviour over time of study variables will be summarised by treatment cohort and overall as follows:

- **Continuous variables:** Descriptive statistics for each time point and for the absolute/percentage differences to baseline.
- **Categorical variables:** Descriptive statistics for each time point and shift tables to baseline.

Correlation among patient's variables will be evaluated calculating the appropriate correlation coefficient with the respective statistical significance level.

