12.1. Efficacy analysis

The following parameters will be summarized by cohort and overall (if appropriate) on the Efficacy population:

- Best Overall Response
- Disease Control Rate
- Objective Response Rate
- Duration of response (DoR)
- Progression Free survival (PFS);
- Overall Survival (OS).

ORR locally assessed is the primary endpoint of the Cohort Expansion Phase. All efficacy

endpoints related to tumour assessment will be evaluated considering both local (secondary endpoints) and central (exploratory endpoints) radiology assessments.

Best Overall Response (BOR) is derived as follows:

- If a subject has at least one overall response of CR, then BOR is CR;
- If a subject doesn't have any overall response of CR but has at least one overall response of PR, then BOR is PR;
- If a subject doesn't have any overall response of CR or PR but has at least one overall response of SD (or Non-CR / Non-PD) at least six weeks after the first intake of MEN1611, then BOR is SD (or Non CR / Non PD);
- If a subject doesn't have any overall response of CR, PR, SD (or Non-CR / Non-PD) after at least 6 weeks from the first intake of MEN1611, but has at least one overall response of PD, then BOR is PD;
- In all other cases, BOR is NE.

Objective Response Rate (ORR) is calculated as the sum of BOR rates of complete response (CR), partial response (PR).

Disease Control Rate (DCR) is calculated as the sum of BOR rates of complete response (CR), partial response (PR) and stable disease (SD).

Overall Survival (OS) is calculated as:

- In case of all-cause death:
OS = date of death - date of first study treatment administration + 1;
- In case of censored information not for drop-out:
OS = date of end of observation period (i.e. maximum between end of study and last follow up date) - date of first study treatment administration + 1;
- In case of censored information for drop-out:
OS = last available date in eCRF - date of first study treatment administration + 1.

Progression-free Survival (PFS) is calculated as:

- In case of death/disease progression:
PFS = date of death or date of first disease progression - date of first study treatment administration + 1
For subjects who experienced both death and progression disease, the date referred to the event that came first is considered.
- In case of censored information due to responding subjects or lost to follow-up:
PFS = date of censoring - date of first study treatment administration + 1

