Detailed censoring rules are as follows:

Circumstances		Options for end-date (progression or censoring)	Outcome
1	Documented Progression	(i) Date of documented progression	Progressed
2	Death without documented progression	(i) Date of death	Progressed
3	Documented progression or death after exactly one missing assessment	(i) Date of progression or death	Progressed
4	Documented progression or death after two or more missing assessments	(i) Date of last adequate assessment ^a	Censored
5	No documented progression and no death (with at least one post baseline assessment)	(i) Date of last adequate assessment	Censored
6	Treatment discontinuation Reason ' Disease progression/clinical progression/progression ' without radiological assessment.	(i) Ignore clinical progression and follow situations above	As per above circumstances
7	No baseline tumor assessment	Date of first study treatment administration	Censored
8	No post baseline assessment and no death	Date of first study treatment administration	Censored
9	Subject lost to follow-up (or withdrew consent) before documented progression or death	(i) Date of last adequate assessment	Censored

^aAfter the last adequate tumor assessment. Date of next scheduled assessment- as specified in the protocol

Duration of Response (DR) is calculated as:

- In case of disease progression:
DR = date of disease progression – date of first occurrence of a BOR of PR, CR or SD + 1
- In case of censored information:
DR = date of last tumor assessment – date of first occurrence of a BOR of PR, CR or SD + 1

Note: subjects with only one assessment post baseline with response equal to PD won't be counted for the DR calculation

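### The Step 2 primary ORR, and DCR, PFS and OS, leave out patients who fail before completing two cycles instead of counting them as failures

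*SAP*

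**What the plan says.** SAP 7.3 defines the Efficacy population as "all eligible patients who receive at least 2 complete treatment cycles and have at least 1 disease assessment", and Protocol 9.2 gives the same definition. SAP 12.1 applies it to every listed efficacy endpoint: "The following parameters will be summarized by cohort and overall (if appropriate) on the Efficacy population". The list covers best overall response (BOR), DCR, ORR, duration of response, PFS and OS. Locally assessed ORR is the Step 2 primary endpoint.

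Four other provisions bear on the point:

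- Protocol 8.2.3.2 makes progression a ground for stopping study treatment and foresees "Unscheduled assessments showing disease progression and leading to" withdrawal.
- SAP 12.1 has rules for early failures. The PFS censoring table treats "Death without documented progression" as an event (rule 2) and has a row for "No post baseline assessment and no death" (rule 8). A patient who fits no other response category has a BOR of NE.
- Protocol 8.2.4 limits survival follow-up after the End of Study Visit to patients evaluable for efficacy.
- The synopsis (Study Duration) counts the target of 40 in evaluable, not treated, patients.

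**The concern.** Membership of the analysis set depends on what happens after the first dose. A patient who cannot complete two cycles because the disease progressed, because of toxicity or because of death is a treatment failure, yet the definition removes that patient before the NE category or PFS rule 2 can apply. Some of these outcomes are known, not missing: a patient with progression on an unscheduled scan in Cycle 1 has an assessment but not the required cycles.

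With no comparator, the denominator directly sets the reported ORR and DCR. PFS and OS are counted from first dose, but on this set they are conditional on the patient having reached at least Cycle 2. SAP 12 makes efficacy descriptive, so the harm is a biased estimate, not an inflated type I error.

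**Working it through.** **Plan's own figure.** The target of 40 evaluable patients cannot be reproduced, because the sample size text is redacted in both documents. That is not a fault of the plan. It means that no assumed non-evaluable share is visible.

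**Step 1: who is lost.** Neither document defines a *complete* cycle. The only counting rule, in SAP 11.5.2 on exposure, counts a cycle once any dose of either drug is given in it. Both readings are shown.

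| Patient | One dose per cycle suffices | Two full cycles needed |
|---|---|---|
| Dies, progresses or stops in Cycle 1 (no Cycle 2 dose) | out | out |
| Dosed in Cycle 2, progression on an unscheduled scan, treatment stopped before the cycle ends | in | out |
| Dosed in Cycle 2, dies in that cycle with no post-baseline scan | in only if the baseline scan counts | out |
| Two full cycles, no later scan | in only if the baseline scan counts | in only if the baseline scan counts |
| Two full cycles, progression at the Cycle 3 scan | in, as PD | in, as PD |

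The first row is lost on either reading.

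**Step 2: effect on OS and PFS, with no assumed rates.** Cycles last 28 days, so the nominal study days are:

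- Cycle 2 Day 1 = 28 + 1 = 29
- Cycle 2 Day 22 (last Cycle 2 infusion) = 28 + 22 = 50
- Cycle 2 Day 28 = 28 + 28 = 56
- Cycle 3 Day 1 = 56 + 1 = 57, so the 7-day scan window opens on day 57 − 7 = 50

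SAP 11.2 reports "Kaplan-Meier survival curves and event rate every 28 days" for time-to-event variables. Entry to the set needs at least one Cycle 2 dose, on day 29 or later, so nobody in it can have died by day 28. The OS event rate at day 28 is 0% whatever the drug does. If two full cycles are needed, it stays 0% to about day 50 or 56. PFS before day 50 behaves in the same way on that reading, provided treatment is stopped at progression as Protocol 8.2.3.2 says.

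**Step 3: effect on ORR and DCR, illustration only.** The exclusion share d is an assumption, taken as 5% to 30%. All treated N = 40/(1 − d), rounded up: 40/0.95 gives 43 and 40/0.70 gives 58. The realised shares are 3/43 = 7.0% and 18/58 = 31.0%. The 8 responders and 22 patients with disease control among the 40 are hypothetical. Intervals are exact (Clopper-Pearson) 95%.

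| Quantity | Evaluable, N = 40 | All treated, N = 43 | All treated, N = 58 |
|---|---|---|---|
| ORR, no responder excluded | 8/40 = 20.0% (9.1 to 35.6) | 8/43 = 18.6% (8.4 to 33.4) | 8/58 = 13.8% (6.1 to 25.4) |
| ORR, one responder excluded | 8/40 = 20.0% | 9/43 = 20.9% (10.0 to 36.0) | 9/58 = 15.5% (7.3 to 27.4) |
| DCR, none of the excluded controlled | 22/40 = 55.0% | 22/43 = 51.2% | 22/58 = 37.9% |
| DCR, one third of the excluded controlled | 22/40 = 55.0% | 23/43 = 53.5% | 28/58 = 48.3% |

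When no responder is excluded, the evaluable ORR equals the all-treated ORR divided by (1 − d), with d the realised share.

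**The case against.** The definition is prespecified, identical in both documents and used only for description. The strongest arguments for leaving it are these.

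- **The loss may be small.** If the SAP 11.5.2 counting rule applied, a patient dosed in Cycle 2 who then progressed with a scan would stay in. That rule serves exposure and does not define a complete cycle. Even under it, everyone without a Cycle 2 dose is lost. What stands is that the undefined term determines how many patients go.
- **Few progressions can be seen before about day 50.** The first scheduled scan window opens then, so earlier RECIST progression needs an unscheduled scan. Part of the low early PFS event rate comes from the scan schedule, which an all-treated analysis would share. This stands for PFS, but not for deaths or toxicity stops.
- **Some unassessed patients may remain.** The required disease assessment is not said to be post-baseline. If a baseline scan counts, a patient with two cycles and no later scan stays in as NE. This stands as an ambiguity.
- **The sizes are assumed.** This is correct: the shift could be slight, and with 3 exclusions a single excluded responder reverses it.
- **The information is partly recoverable.** SAP 11.4 tabulates the population counts, Table 1.3 gives withdrawal reasons, and Listings 5.29 and 5.30 give response by timepoint. A reader could rebuild much of ORR and DCR, but the plan contains no such estimate. For survival, the documents show only that later follow-up of excluded patients is not planned, not that it is unobtainable.
- **Redaction.** The Step 2 design, sample size and exploratory endpoints are hidden and may hold a rationale. The titles of the five efficacy tables (3.1.1 to 3.3) name no population, so they neither show nor rule out a second one. SAP 12.1 names only the Efficacy population.

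**Conclusion.** The concern holds. On the visible text, the Step 2 primary ORR and the other listed efficacy endpoints exclude early failures, and nothing restores them. The day-28 OS event rate of 0% follows from the definition alone. The likely direction is upward for ORR and DCR and longer for PFS and OS.

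The size is unknown. In the illustration, ORR falls by 20.0 − 18.6 = 1.4 to 20.0 − 13.8 = 6.2 percentage points if no excluded patient responded. That rests on assumed exclusion shares and a hypothetical responder count. Confidence is high on the wording and its consequence, and low on the magnitude. It should be fixed, but it does not invalidate the trial.

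**What to change.** 1. Make the Safety population (at least one dose of MEN1611) the main set for ORR, DCR, PFS and OS, by dose cohort. Count patients without a post-baseline assessment as non-responders and as without disease control.
2. Keep the two-cycle set, which matches the target of 40, as a supportive analysis shown alongside.
3. State how treated but ineligible patients are handled, since the current set also drops them.
4. Keep PFS rule 2 unchanged.
5. Extend the 12-weekly survival follow-up to all treated patients while the study runs.
6. Define a complete cycle and state that the disease assessment must be post-baseline.

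Two optional additions would help the reader: the number of patients censored at first dose under PFS rules 7 and 8, and a sensitivity analysis that counts clinical progression as an event, because rule 6 says "Ignore clinical progression and follow situations above".

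The cost is SAP wording, one further set of tables, status calls for early drop-outs, and the substantial protocol amendment that Protocol 9.5 requires when the primary analysis changes. If the wider follow-up alters the consent terms, Protocol 5.3 also requires an updated consent form. Headline ORR and DCR would probably be somewhat lower. The population, the NE category and the censoring rules already exist.
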